6.3. Other Secondary Endpoints

6.3.1. Pharmacokinetic/Pharmacodynamics

The following pharmacokinetic analyses will be based on the PK analyses set by treatment group using the data from Phase 1b and Phase 2.

6.3.1.1. Pharmacokinetic Concentrations

Pharmacokinetic blood samples for determination of PF-07901801, tafasitamab and lenalidomide concentrations will be collected in accordance with the regimen specified in the schedule of events. The concentrations as reported by the bioanalytical lab will be used without rounding for all analyses.

For concentration data, all values below the limit of quantification (BLQ) will be set to 0 for summary statistics and graphs. Individual concentrations of PF-07901801, tafasitamab and lenalidomide will be summarized by dose levels (or treatment groups) at each time point using descriptive statistics. Individual concentration plots and median data by dose levels (or treatment groups) graphs will be produced. All graphs will be presented using both linear and semi-logarithmic scales.

The below precision will be used for descriptive and statistical summary of PF-07901801, tafasitamab and lenalidomide concentrations:

- Geometric Means, Medians and their %CV and Confidence Intervals (CIs) – 1 more significant figure than the data
- Standard Deviation – 1 more significant figure than means
- CV% – whole numbers
- Minimum, Maximum – same significant figures as the data
- Ratios, CIs (log transformed data) – 2 decimal places

All PF-07901801, tafasitamab and lenalidomide concentrations will be presented in a by-patient listing. Additionally, time elapsed since dosing and deviation from scheduled time point will be presented.

6.3.1.2. Pharmacokinetic Parameters

The PK data from this study may be used to develop a population PK model and may also be pooled with other studies for population PK model analysis. The correlations between PF-07901801, tafasitamab and lenalidomide exposure parameters and pharmacodynamic biomarker, efficacy and/or safety outcomes may be explored if data allows. The results of these modeling analyses will be reported separately from the clinical study report.

The potential drug-drug interactions between PF-07901801, tafasitamab, and/or lenalidomide will also be evaluated if data allows.

6.3.2. Immunogenicity

The following analyses of immunogenicity data will be based on the Immunogenicity analysis set by treatment group using the data from Phase 1b and Phase 2.

Final individual subject results from the ADA and NAb assay (as appropriate) will be presented in the listings and the incidence summarized by descriptive statistics in tabular form by dose levels (or treatment groups).

Summary tables that show the number and percentage of subjects that fall into the following categories will also be produced by dose levels (or treatment groups):

Treatment-induced ADA	Baseline ADA titer is missing or negative and subject has ≥ 1 post-treatment positive ADA titer.
Treatment-boosted ADA	Baseline ADA titer is positive, and subject has a ≥ 4 -fold dilution increase in ADA titer from baseline in ≥ 1 post-treatment sample. If ADA titer is log ₁₀ transformed, a 4-fold dilution increase is equivalent to 0.602 unit increase in titer (log ₁₀) from baseline. If ADA titer is log ₂ transformed, a 4-fold dilution increase is equivalent to 2 unit increase in titer (log ₂) from baseline.
ADA-positive subject	A subject with ≥ 1 treatment-induced or treatment-boosted ADA response.
ADA-negative subject	An ADA evaluable subject without treatment-induced or treatment-boosted ADA response. Subject either has (1) all ADA-negative results

	throughout the study or (2) is ADA positive at baseline but did not become treatment-boosted post-dose.
ADA incidence	The percent of ADA-positive subjects in a treatment group/cohort or study.
Treatment-induced NAb	Baseline NAb titer is missing or negative or ADA-negative and subject has ≥ 1 post-treatment positive NAb titer.
Treatment-boosted NAb	Baseline NAb titer is positive and subject has a ≥ 4 -fold dilution increase in NAb titer from baseline in ≥ 1 post-treatment sample. If NAb titer is log ₁₀ transformed, a 4-fold dilution increase is equivalent to 0.602 unit increase in titer (log ₁₀) from baseline. If NAb titer is log ₂ transformed, a 4-fold dilution increase is equivalent to 2 unit increase in titer (log ₂) from baseline.
NAb-positive subject	An ADA-positive subject with ≥ 1 treatment-induced or treatment-boosted NAb response. For ADA-positive (treatment-boosted) subjects, subject is NAb positive only if the subject has ≥ 1 treatment-induced or treatment-boosted NAb response at the visit where the subject has a treatment-boosted ADA response. For visits where the subject did not show a boosted ADA response, the subject is classified as NAb-negative for the visit even if the subject has post-treatment positive NAb titer for that visit.
NAb-negative subject	NAb evaluable participant who is either (1) an ADA-negative subject or (2) an ADA-positive subject without treatment-induced or treatment-boosted NAb response (i.e. subject has all NAb-negative results throughout the study or subject is NAb positive at baseline but did not become treatment-boosted post-dose). Note: in the event a subject is ADA-positive at baseline but did not show a boosted response post-treatment, subject is classified as ADA-negative and NAb-negative at the subject level even if the subject has post-treatment positive NAb titer. As such all ADA-negative subjects are NAb-negative regardless of NAb titer data.
NAb incidence	The percent of NAb-positive subjects in a treatment group/cohort or study.
Transient ADA	An ADA-positive subject with (1) a treatment-induced or treatment-boosted ADA sample detected only at 1 sampling time (excluding the last time point) post-treatment, or (2) treatment-induced or treatment-boosted ADA samples detected at ≥ 2 time points where the first and last positive samples (irrespective of any negative samples in between) are separated by < 16 weeks, and the subject's last sample is ADA negative.
Persistent ADA	An ADA-positive subject with first and last positive ADA samples (treatment-induced or treatment-boosted) detected over a period of ≥ 16 weeks post-treatment, irrespective of any negative samples in between.
Indeterminate ADA	An ADA-positive subject who is not persistent or transient.
Transient NAb	A NAb-positive subject with (1) a treatment-induced or treatment-boosted NAb sample detected only at 1 sampling time (excluding the last

	time point) post-treatment, or (2) treatment-induced or treatment-boosted NAb samples detected at ≥ 2 time points where the first and last positive samples (irrespective of any negative samples in between) are separated by < 16 weeks, and the subject's last sample is NAb negative or ADA negative
Persistent NAb	A NAb-positive subject with first and last positive NAb samples (treatment-induced or treatment-boosted) detected over a period of ≥ 16 weeks post-treatment, irrespective of any negative samples in between.
Indeterminate NAb	A NAb-positive subject who is not persistent or transient.

Titers will be reported as median, range and interquartile range if applicable.

Descriptive summaries (mean, standard deviation, median, and range) of time to ADA response will be presented by dose levels (or treatment groups) if applicable.

6.4. Exploratory Endpoints

6.4.1. Biomarker Analysis

CCI

Exploratory biomarker endpoints will not be reported in CSR. Results of exploratory endpoint analyses will be disseminated to the scientific community to the extent possible through presentation at scientific meetings and/or publication in peer-reviewed scientific journals.

6.5. Subset Analyses

All the subset analyses will be exploratory, no adjustment for multiplicity will be performed. Analyses will only be performed if there is sufficient sample size. As a general rule, subset analysis will only be performed if there are ≥ 10 participants overall within the defined subset. Deviations from these analyses will be described in the clinical study report.

ORR and DoR (if meaningful) will be summarized in the following subsets within each treatment group using the data from Phase 2.

- Prior anti-cancer therapy (CAR-T vs others)
- Lines of prior therapies (1 vs ≥ 2)
- IPI score (≤ 3 vs > 3)
- Response to most recently administered prior anti-cancer therapy (CR/PR vs SD/PD)
- Classification based on molecular profiling (GCB, ABC, unclassified)

6.6. Baseline and Other Summaries and Analyses

6.6.1. Baseline Summaries

The following analyses will be based on the Safety Analysis Set overall and separately by treatment group.

6.6.1.1. Demographic Characteristics

The following demographic and baseline characteristics will be summarized:

- Gender (Male, Female)
- Age (years): summary statistics
- Age categories (<70, \geq 70)
- Race (White, Black or African American, Asian, American Indian or Alaska Native, Native Hawaiian or other Pacific Islander, Other, Unknown)
- Ethnicity (Hispanic, Not Hispanic, Not reported)
- Geographical Region (North America, Europe, Asia, Rest of the World)
- Physical measurements
 - Height (cm)
 - Weight (kg)
 - Body Mass Index (BMI) (kg/m^2)
- ECOG Performance Status

Site codes will be used for the determination of the patient's geographic region.

The listing of demographics and baseline characteristics will include the following information: patient identifier, treatment group, age, sex, race, ethnicity, height (cm), weight (kg), BMI (kg/m^2) and ECOG.

6.6.1.2. Medical History

Medical history will be coded using the most current available version of Medical Dictionary for Regulatory Activities (MedDRA) and will be summarized from the 'Medical History' eCRF page. Medical history will be summarized as the numbers and percentages of patients by MedDRA preferred term (PT) as event category and MedDRA primary system organ class (SOC) as summary category. Each patient will be counted only once within each PT or SOC.

Medical history will be displayed in terms of frequency tables: ordered by primary SOC and PT in alphabetical order.

6.6.1.3. Disease Characteristics

The following baseline disease characteristics will be summarized using information collected on the 'Primary Diagnosis' and Tumor Assessment eCRF pages, as well as molecular biomarker pages:

- Current histopathological classification
- Classification based on molecular profiling (GBC, ABC, unclassified)
- Stage - initial diagnosis
- Stage - Current
- IPI score
- Time since initial histopathological diagnosis to 'start date' (months), defined as ('start date' – date of initial histopathological diagnosis)/30.4375
- Time since most recent recurrence/metastatic (months), defined as ('start date' – date of most recent recurrence/metastatic)/30.4375
- Involved tumor sites at baseline
- Response to first line of prior anti-cancer therapy
- Response to the most recently administered prior anti-cancer therapy
- Bulky disease (defined as any target lesion with the longest diameter $\geq 7.5\text{cm}$)

Listing of disease history will be provided with all relevant data (as collected on the 'Primary Diagnosis' and Tumor Assessment eCRF pages) and derived variables as above.

6.6.1.4. Prior Anti-cancer Therapies

The prior anti-cancer therapies are collected under the 'Prior Cancer Therapy', 'Radiation' and 'Cancer Surgery' eCRF pages.

The number and percentage of patients in each of the following anti-cancer therapy categories will be tabulated:

- Patients with at least one type of prior anti-cancer therapy
- Patients with at least one prior anti-cancer drug therapy
- Patients with at least one prior anti-cancer radiotherapy (curative/palliative)

- Patients with at least one prior anti-cancer surgery
- Patients with at least one prior transplant
- Patients with prior CAR-T

Prior anti-cancer drug therapy will be summarized as follows based on the number and percentage of patients with the following:

- At least one prior anti-cancer drug therapy
- Number of prior anti-cancer drug therapy regimens: missing / 1 / 2 / 3 / 4 / ≥ 5

The prior anti-cancer drug therapies will also be summarized based on the number and percentage of patients by the drug class and preferred term. A patient will be counted only once within a given drug class and within a given drug name, even if he/she received the same medication at different times. The summary will be sorted on decreasing frequency of drug class and decreasing frequency of drug name in a given drug class. In case of equal frequency regarding drug class (respectively drug name), alphabetical order will be used.

Prior anti-cancer therapies will be included in the listings that follow with a flag to identify prior therapies. These will include the patient identification number, and all the relevant collected data-fields on the corresponding eCRF pages.

- Listing of anti-cancer drug therapies
- Listing of anti-cancer radiotherapy (curative/palliative)
- Listing of transplant
- Listing of anti-cancer surgeries

6.6.2. Study Conduct and Participant Disposition

The following analyses will be performed based on the Safety Analysis Set overall and separately by treatment group for Phase 1b and Phase 2 separately.

6.6.2.1. Disposition

The percentages below will be calculated based on the number of patients in the Safety Analysis Set.

- Total number of patients screened overall
- Number of patients enrolled/randomized into the study

- Number of patients who discontinued from the study prior to treatment with study drug overall and by the main reason for discontinuation
- Number and percentage of patients in each of the analysis sets defined in Section 4
- Number and percentage of patients with study drug ongoing (separately for each study drug when administered in combination)
- Number and percentage of patients who discontinued study drug overall and by the main reason for discontinuation of study drug (separately for each study drug when administered in combination)
- Number and percentage of patients who entered follow-up
- Number and percentage of patients who discontinued follow-up overall and by the main reason for discontinuation

In addition the following will be summarized:

- Number and percentage of treated patients overall, by region (Europe, EEA (required by EudraCT), North America, Latin America, Middle East, Asia, Australasia, Africa), by country within region
- Number and percentage of treated patients by center

Dispositions related to COVID-19 may be presented in a separate listing if there is significant impact of COVID-19.

6.6.2.2. Protocol Deviations

Potentially important protocol deviations will be compiled prior to database lock. Potentially important protocol deviations will be summarized by category (n[%]) for the Safety Analysis Set.

In addition, protocol deviations related to COVID-19 may be presented in a separate listing if there is significant impact of COVID-19.

6.6.3. Study Treatment Exposure and Compliance

The following analyses will be based on the safety analysis set by treatment group.

Cycle definitions for study drugs that are administered in combination apply to all the study drugs in the combination. Ie, cycle is patient-dependent, rather than study-drug-dependent when study drugs are administered in combination.

For Cycle X, actual cycle start date for each patient is

- the earliest start date of dosing in the Cycle X day 1 visit eCRF exposure page, if the patient received study treatment on that visit (ie, any study drug with dose>0 at that visit)
- the first day of assessments in the Cycle X day 1 visit, if the patient did not receive study treatment on that visit (ie, all study drugs had dose=0 at that visit). Use start date in the exposure page if available; if start date is not available then use date of collection of vital signs on Cycle X day 1 visit.

Actual cycle end date for each patient is,

- for all cycles X except the last cycle, actual cycle end date = actual cycle (X+1) start date – 1 day;
- for the last cycle, actual cycle end date = actual cycle start date + 28 (in days) – 1 day

Cycle duration (weeks) = (actual cycle end date – actual cycle start date + 1)/7

When summarizing exposure for each study drug, only cycles from first dose of study treatment until the last cycle with non-zero dose of at least one of the study drugs should be included.

Exposure will be summarized as dose received (duration of exposure, cumulative dose, actual dose intensity) and as dose received relative to intended dose (relative dose intensity [RDI]).

The information that will be summarized depends on how the study drug is dosed (eg, infusion cyclical, oral daily, oral cyclical).

The formulae below should be applied to each study drug separately even when study drugs are administered in combination.

6.6.3.1. Exposure to PF-07901801

Phase 1b:

The dose level for PF-07901801 is calculated as actual dose administered/weight (mg/kg). The last available weight of the patient on or prior to the day of dosing will be used.

PF-07901801 will be administered weekly (QW) during Cycle 1, 2, and 3, then bi-weekly (Q2W). Each cycle is 28 days (4 weeks).

Cohort	Dose (mg/kg)
1 (DL1)	4 mg/kg QW for C1 to C3 then Q2W
2 (DL2)	10 mg/kg QW for C1 to C3 then Q2W
3 (DL3)	18 mg/kg QW for C1 to C3 then Q2W

Intended duration of treatment with PF-07901801 (weeks) =

(end date–date of first dose of study drug +1) (days) / 7(days/week),

where end date = start date of last cycle with non-zero dose of study drug + 28 – 1

Duration of exposure to PF-07901801 (weeks) =

(last dose date - first dose date + d) (days) / 7 (days/week),

where d is the number of days based on the maximum number of cycles of PF-07901801 started and defined as following.

- For patients who started 3 cycles or less: d=7 days,
- For patients who started Cycle ≥ 4 : d = 14 days.

Cumulative dose (mg/kg) is the sum of the actual doses of PF-07901801 received.

Intended cumulative dose (mg/kg) is based on the maximum number of cycles of PF-07901801 started and defined as following

- For patients who started no more than 3 cycles:
 - Intended cumulative dose (mg/kg)= $DL(\text{mg/kg}/\text{dose}) * 4 (\text{doses}/\text{cycle}) * \text{Number of Cycles started}$.
- For patients who started maximum Cycle i, where $i \geq 4$:
 - Intended cumulative dose (mg/kg) = $DL(\text{mg/kg}/\text{dose}) * 4 (\text{doses}/\text{cycle}) * 3 (\text{cycles}) + DL(\text{mg/kg}) * 2 (\text{doses}/\text{cycle}) * (i-3) (\text{cycles}) = DL(\text{mg/kg}/\text{dose}) (2i+6) (\text{doses})$

Actual Dose Intensity (DI)

- Overall actual DI (mg/kg/4-week cycle) = [overall cumulative dose (mg/kg)] / [intended duration of treatment with PF-07901801 (weeks)/4].

Relative Dose Intensity (RDI)

- Intended DI (mg/kg/4-week cycle) = [intended cumulative dose (mg/kg)] / [intended duration of treatment with PF-07901801 (weeks)/4]
- Overall RDI (%) = $100 \times [\text{overall actual DI}] / [\text{intended DI}]$

Phase 2:

Up to 2 fixed doses of PF-07901801 will be explored in Phase 2.

The dose level for PF-07901801 is calculated as actual dose administered (mg).

PF-07901801 will be administered weekly (QW) during Cycle 1, 2, and 3, then bi-weekly (Q2W). Each cycle is 28 days (4 weeks).

Intended duration of treatment with PF-07901801 and duration of exposure of PF-07901801 are calculated in the same way as that for Phase 1b.

Cumulative dose (mg) is the sum of the actual doses of PF-07901801 received.

Intended cumulative dose (mg) is based on the maximum number of cycles of PF-07901801 started and defined as following

- For patients who started no more than 3 cycles:
 - Intended cumulative dose (mg) = $DL(\text{mg/dose}) * 4 \text{ (doses/cycle)} * \text{Number of Cycles started.}$
- For patients who started maximum Cycle i , where $i \geq 4$:
 - Intended cumulative dose (mg) = $DL(\text{mg/dose}) * 4 \text{ (doses/cycle)} * 3 \text{ (cycles)} + DL(\text{mg/dose}) * 2 \text{ (doses/cycle)} * (i-3) \text{ (cycles)}$

Actual Dose Intensity (DI)

- Overall actual DI (mg/4-week cycle) = [overall cumulative dose (mg)] / [intended duration of treatment with PF-07901801 (weeks)/4].

Relative Dose Intensity (RDI)

- Intended DI (mg/4-week cycle) = [intended cumulative dose (mg)] / [intended duration of treatment with PF-07901801 (weeks)/4]
- Overall RDI (%) = $100 \times [\text{overall actual DI}] / [\text{intended DI}]$

6.6.3.2. Exposure to Tafasitamab

The dose level for tafasitamab is calculated as actual dose administered/weight (mg/kg). The last available weight of the patient on or prior to the day of dosing will be used.

Tafasitamab will be administered at 12 mg/kg IV according to the following schedule: each cycle has 28 days.

- C1: Days 1, 4, 8, 15 and 22.
- C2 and C3 (QW): Days 1, 8, 15 and 22.
- $\geq C4$ (Q2W): Days 1 and 15.

Intended duration of treatment with tafasitamab (weeks) =

(end date–date of first dose of study drug +1)/7,

where end date = start date of last cycle with non-zero dose of study drug + 28 – 1

Duration of exposure to tafasitamab (weeks) =

(last dose date - first dose date + d) (days) / 7 (days/week),

where d is the number of days based on the maximum number of cycles of tafasitamab started and defined as following.

- For patients who started only Cycle 1:
 - d=3, if only Day 1 dose received;
 - d=4, if the last day the dose received is Day 4;
 - d=7, if the last day the dose received is Day 15 or Day 22.
- For patients who started Cycle 2 or 3: d = 7 days;
- For patients who started Cycle ≥ 4 : d = 14 days.

Cumulative dose (mg/kg) is the sum of the actual doses of tafasitamab received.

Intended cumulative dose (mg/kg) is based on the maximum number of cycles of tafasitamab started and defined as following

- For patients who started Cycle 1 only:
 - Planned cumulative dose (mg/kg) = $5*12 \text{ mg/kg} = 60 \text{ mg/kg}$
- For patients who started no more than Cycle 2:
 - Planned cumulative dose (mg/kg) = $5*12 \text{ mg/kg} + 4*12 \text{ mg/kg} = 108 \text{ mg/kg}$
- For patients who started no more than Cycle 3:
 - Planned cumulative dose (mg/kg) = $5*12 \text{ mg/kg} + 4*12 \text{ mg/kg} + 4*12 \text{ mg/kg} = 156 \text{ mg/kg}$
- For patients who started no more than Cycle i , where $i \geq 4$:
 - Planned cumulative dose (mg/kg) = $156 \text{ mg/kg} + (i-3)*2*12 \text{ mg/kg} = 156 \text{ mg/kg} + (i-3)*24 \text{ mg/kg} = (i*24 + 84) \text{ mg/kg}$

Actual Dose Intensity (DI)

- Overall actual DI (mg/kg/4-week cycle) = [overall cumulative dose (mg/kg)] / [intended duration of treatment with tafasitamab (weeks)/4].

Relative Dose Intensity (RDI)

- Intended DI (mg/kg/4-week cycle) = [intended cumulative dose (mg/kg)] / [intended duration of treatment with tafasitamab (weeks)/4]
- Overall RDI (%) = $100\% \times [\text{overall actual DI}] / [\text{intended DI}]$

6.6.3.3. Exposure to Lenalidomide

The dose level is calculated as actual dose administered (mg/day).

Lenalidomide will be administered 25 mg PO daily on Days 1 through 21 of each 28-day cycle for up to 12 cycles.

Intended duration of treatment lenalidomide (weeks) =

$$(\text{end date} - \text{date of first dose of study drug} + 1) / 7,$$

where end date = start date of last cycle with non-zero dose of study drug + 28 – 1.

Duration of exposure to lenalidomide (weeks) =

$$(\text{last dose date of lenalidomide} - \text{first dose date of lenalidomide} + 7) / 7$$

Cumulative dose (mg) is the sum of the actual doses of lenalidomide received in the study.

Actual Dose Intensity (DI)

- Overall actual DI (mg/4-week cycle) = Cumulative dose (mg) / Duration of exposure to lenalidomide (weeks) / 4 (weeks/cycle)

Intended Dose Intensity (DI)

- Overall intended DI (mg/4-week cycle) = 25 (mg/day) \times 21 (days/4-week cycle) = 525 (mg/4-week cycle).

Relative Dose Intensity (RDI)

- RDI (%) = [Overall actual DI (mg/4-week cycle) / Overall intended DI (mg/4-week cycle)] \times 100% = [Overall actual DI (mg/4-week cycle) / 525 (mg/4-week cycle)] \times 100%

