### 6.1.1. Administration

For this study, a cycle is defined as 28 days, regardless of missed doses or dose interruptions.

Administration of PF-07901801 and tafasitamab may be performed on an outpatient basis. There is a risk of allergic reactions, including anaphylaxis shock, thus these infusions are to be administered in a setting that allows for immediate access to an intensive care unit or equivalent environment and administration of therapy for anaphylaxis, such as the ability to implement immediate resuscitation measures.

PF-07901801 and tafasitamab drug products will be diluted and administered as per the IP Manual.

Body weight for dosing of PF-07901801 (in part 1b of the study) and tafasitamab can be measured up to 72 hours prior to administration on Day 1 of each cycle. This baseline weight will be used to calculate the subsequent dose(s) during the given cycle provided the weight does not deviate more than  $\pm 10\%$  from baseline during the course of this cycle. In cases

where the participant's body weight changes more than  $\pm 10\%$  from baseline, the current weight will be used to calculate the next and subsequent doses of drug. Using body weight prior to each infusion is also allowed, if this is the investigator's usual standard of care.

Pre-infusion safety laboratory test results must be reviewed prior to dosing, per dosing schedule.

Qualified and trained investigator site personnel will administer PF-07901801 and tafasitamab to participants by IV infusion. During and following each infusion, the participants will be monitored closely for signs and symptoms of an IRR. In case of IRRs or other adverse reactions, consult the recommended dose modifications provided in [Table 9](#).

On days in which PF-07901801 and tafasitamab are administered on the same day, PF-07901801 is administered first.

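### Lenalidomide RDI sets dose per time on drug against a full 28-day cycle, so it exceeds 100% at full compliance and is inflated by permanent mid-cycle stops

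*SAP*

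**What the plan says.** SAP 6.6.3.3 gives the regimen as "Lenalidomide will be administered 25 mg PO daily on Days 1 through 21 of each 28-day cycle for up to 12 cycles". It then defines two durations:

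- "Intended duration of treatment lenalidomide (weeks"), which runs to Day 28 of the last cycle with a non-zero dose. No later formula in the section uses it.
- "Duration of exposure to lenalidomide (weeks"), which is last dose date minus first dose date plus 7 days, in weeks.

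Actual dose intensity (DI) uses the second: "Overall actual DI (mg/4-week cycle) = Cumulative dose (mg) / Duration of exposure to lenalidomide (weeks) / 4 (weeks/cycle"). Intended DI is fixed at "525 (mg/4-week cycle"), and RDI is the ratio of the two.

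For PF-07901801 the actual DI is "overall cumulative dose (mg/kg)] / [intended duration of treatment with PF-07901801 (weeks)/4", so it uses the intended duration. SAP 6.6.3.2 does the same for tafasitamab. For both drugs, intended DI is the intended cumulative dose over that same duration. The SAP gives no reason for treating lenalidomide differently. The opening of SAP 6.6.3 presents RDI as the measure of dose received against dose intended.

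**The concern.** The numerator and the comparator of the lenalidomide RDI rest on different time bases. The comparator spreads 21 doses over 28 days, including 7 rest days. The actual DI spreads the doses taken over the time to the last capsule plus 7 days. Planned dosing ends on Day 21, so even a complete cycle falls one day short of 28. When a participant stops for good part-way through the dosing block, dose and time shrink together while the comparator does not move.

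The stake is a descriptive exposure table. Lenalidomide is the drug that Protocol 6.6 and Table 6 restart at a lower dose after shared cytopenias, so readers will look at its RDI. Phase 2 has been cancelled, but the Phase 1b exposure summary remains. With approximately 20 participants planned across the dose levels, one or two mid-cycle stops can move a group's figure.

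**Working it through.** **Inputs.** 25 mg on Days 1 to 21 (SAP 6.6.3.3). Cycle length from Protocol 6.1.1: "For this study, a cycle is defined as 28 days, regardless of missed doses or dose interruptions". Duration and DI formulas from SAP 6.6.3.1 to 6.6.3.3.

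**The plan's own figure.** Intended DI = 25 × 21 = 525 mg per 4-week cycle, which reproduces.

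**Brackets.** Read strictly left to right, the DI formula gives 525 / (27/7) / 4 = 34.0 mg for one full cycle, an RDI of 6.5%. The unit mg per 4-week cycle requires cumulative dose / (weeks/4), and that reading is used below.

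**Full compliance over c cycles.** Dose = 525c mg. Exposure = 28(c − 1) + 20 + 7 = 28c − 1 days. RDI = 28c / (28c − 1).

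- c = 1: 28/27 = 103.7%
- c = 2: 56/55 = 101.8%
- c = 12: 336/335 = 100.3%

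The PF-07901801 and tafasitamab formulas give exactly 100% at full compliance.

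**Permanent stop after dose k of cycle c, no other missed doses.** Dose = 525(c − 1) + 25k mg. Exposure = 28(c − 1) + k + 6 days. Share of plan = dose / 525c.

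| Last dose | Dose (mg) | Exposure (days) | RDI as written | Share of plan |
|---|---|---|---|---|
| Cycle 1, Day 1 | 25 | 7 | 19.0% | 4.8% |
| Cycle 1, Day 7 | 175 | 13 | 71.8% | 33.3% |
| Cycle 1, Day 14 | 350 | 20 | 93.3% | 66.7% |
| Cycle 1, Day 18 | 450 | 24 | 100.0% | 85.7% |
| Cycle 2, Day 14 | 875 | 48 | 97.2% | 83.3% |
| Cycle 3, Day 3 | 1125 | 65 | 92.3% | 71.4% |
| Cycle 6, Day 14 | 2975 | 160 | 99.2% | 94.4% |
| Cycle 12, Day 14 | 6125 | 328 | 99.6% | 97.2% |

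For a Day 14 stop the gap falls from 26.7 points in Cycle 1 to 13.9 in Cycle 2 and 2.4 in Cycle 12. In any cycle, a final dose on Day 18 gives exactly 100%, and on Day 19 or 20 more than 100%, despite missed doses.

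**Hold with resumption.** Take Days 1 to 7, hold 7 days, then take Days 15 to 21: 14 doses over 27 days. RDI = 350 / (27/28) / 525 = 69.1%, close to the 66.7% taken. The hold is captured.

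**Does swapping in the intended duration match the other drugs?** Not fully. SAP 6.6.3 counts from actual cycle start dates, and Protocol 6.6.2 allows a cycle to start late. Suppose Cycle 2 starts 14 days late and all doses are given. Intended duration = 28 + 14 + 28 = 70 days.

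- Lenalidomide, intended duration, fixed 525 mg: 1050 / (70/28) / 525 = 80%.
- PF-07901801: actual and intended DI share the 70 days, which cancel. 8 of 8 intended doses gives 100%.
- Lenalidomide with an intended cumulative dose of 525 × 2 = 1050 mg: 1050/1050 = 100%.

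**The case against.** The case for leaving this alone has real content. SAP 6.6.3 says that the exposure summary depends on how each drug is dosed, and dose over time on drug is a defensible actual DI. That stands for actual DI taken alone. It does not justify dividing that figure by a full-cycle 525 mg, nor the 7 days where 8 would complete the cycle.

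The excess at full compliance is small, at most 3.7 points. That stands.

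A reader might infer that the RDI hides early stops for toxicity. The documents do not support so strong a reading:

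- The very earliest stops still look poor (19.0% after one dose, 71.8% after seven).
- The effect is the same for progression or withdrawal as for toxicity.
- Holds and dose reductions still lower RDI.
- A stop at a cycle boundary would read 100% under a sound formula too, because intended duration ends with the last cycle dosed.
- Lenalidomide discontinuations by reason (SAP 6.6.2.1), reductions (6.6.3.4), interruptions (6.6.3.5) and the adverse events behind them (6.7.1.1 to 6.7.1.4) all have their own tables.

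A reader might also infer that dose escalation is affected. It is not. Protocol 4.3.4 judges DLT evaluability on actual over planned total dose, which is the undistorted ratio. No endpoint uses RDI.

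**Conclusion.** The formula as written gives wrong values and should be corrected. At full compliance it overstates RDI by 3.7 points after one cycle and 0.3 after twelve. For a permanent stop within the dosing block the overstatement is larger: 38.5 points after 7 doses of Cycle 1 (71.8% against 33.3%), 26.7 after 14, and 14.3 after 18. It fades as cycles accumulate.

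These figures assume brackets as the units require, 28-day cycles started on time, and no other missed or reduced doses. How much the reported summaries would move depends on how many participants stop mid-cycle, which the documents do not say.

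The fault is confined to one descriptive statistic. That the unused intended duration points to a drafting slip is an inference; the SAP does not say so.

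**What to change.** In SAP 6.6.3.3:

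- Intended cumulative dose (mg) = 525 × number of lenalidomide cycles started, maximum 12.
- Actual DI = cumulative dose / [intended duration of treatment with lenalidomide (weeks)/4].
- Intended DI = intended cumulative dose / [intended duration of treatment with lenalidomide (weeks)/4].
- RDI (%) = 100 × actual DI / intended DI.

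This matches PF-07901801 and tafasitamab, returns 100% at full compliance, and settles the brackets.

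If the sponsor prefers to keep the fixed 525 mg per 4 weeks, use the intended-duration denominator with explicit brackets. State that lenalidomide RDI then also reflects cycle delays, unlike the other two drugs. Changing 7 to 8 days alone is not enough: 14 doses in Cycle 1 would still read 350 / (21/28) / 525 = 88.9% against 66.7%.

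The cost is one SAP derivation and no new data. RDI becomes less favourable for participants who stop mid-cycle. Under the matching form, lenalidomide RDI no longer falls when a cycle starts late; SAP 6.6.3.6 would still show such delays for the two infused drugs.
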